- To assess overall survival, complete response rate, duration of response, and duration of overall complete response and duration of stable disease in patients with oligometastatic castration sensitive prostate cancer who initiated the protocol regimen of ADT with SBRT and radium Ra 223 dichloride.
- To assess long-term toxicities during 5-year follow-up in patients with oligometastatic castration sensitive prostate cancer who initiated the protocol regimen of ADT with SBRT and radium Ra 223 dichloride and received at least one dose of radium Ra 223 dichloride

Exploratory Objective

- To perform exploratory analysis of primary or metastatic tumor mutation patterns in this study population at baseline
- To identify immune system factors in the blood that change during the course of ADT-radiotherapy for metastatic prostate cancer
- To describe the rate of normalization of the total alkaline phosphatase level (defined as a return to a value within the normal range) at the end of protocol therapy in patients oligometastatic castration sensitive prostate cancer with total alkaline phosphatase values above the upper limit of the normal range at baseline
- To analyze the patients who were in consideration for the study and the reason for ineligibility, including radiographic review, PSA value, and treatment window.

Study Design

The SHARP study is a single-center open-label, Phase 2 clinical trial of stereotactic body radiation therapy (SBRT), hormone/androgen deprivation therapy (ADT) and radium Ra 223 dichloride for participants with metastatic castration sensitive prostate cancer.

Participants will initiate ADT (LHRH agonist leuprolide or goserelin, or LHRH antagonist degarelix or relugolix) for 4 weeks and then receive 32 weeks of ADT on protocol for a total of 36 weeks. Concurrent with standard of care ADT on protocol participants will receive 1 cycle of SBRT followed by 6 cycles of radium Ra 223 dichloride. SBRT is limited to ≤ 4 metastatic lesions with at least 1 bone lesion. Treatment cycles will be 28 days. Participants will receive bisphosphonate or RANKL inhibitor bone health agents at the dose and schedule consistent with the treatment of bone metastases or prevention of osteoporosis, starting approximately when the protocol therapy is initiated and ending when the patient reaches testosterone recovery (>50 ng/dL) or at the discretion of the PI.

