1.2 Secondary Objectives

- To assess the safety of adding radium Ra 223 dichloride to SBRT and ADT in patients with oligometastatic castration sensitive prostate cancer.
- To assess the Prostate-Specific Antigen (PSA) and overall response rate (ORR) after 6 cycles of radium Ra 223 dichloride (Cycle 8 Day 1)
- To assess the progression-free survival (PFS) in patients with oligometastatic castration sensitive prostate cancer who initiated the protocol regimen of ADT with SBRT and radium Ra 223 dichloride and received at least one dose of radium Ra 223 dichloride.
- To assess time to bone specific PFS in patients with oligometastatic castration sensitive prostate cancer who initiated the protocol regimen of ADT with SBRT and radium Ra 223 dichloride and received at least one dose of radium Ra 223 dichloride.
- To assess overall survival, complete response rate, duration of response, and duration of overall complete response and duration of stable disease in patients with oligometastatic castration sensitive prostate cancer who initiated the protocol regimen of ADT with SBRT and radium Ra 223 dichloride.
- To assess long-term toxicities during 5-year follow-up in patients with oligometastatic castration sensitive prostate cancer who initiated the protocol regimen of ADT with SBRT and radium Ra 223 dichloride and received at least one dose of radium Ra 223 dichloride

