2.5 Bone Health Agents

To optimize treatment with androgen deprivation therapy, Ra-223 and SBRT, we must minimize risk of adverse events. In particular, non-pathologic fractures are an area of concern. Patients on this study are required to take bone health agents (BHAs) including bisphosphonates or RANKL inhibitors, from the start of protocol therapy (approximately) until the participant's testosterone levels are within the normal range or at the discretion of the PI.

The present study is a phase II trial on the use of Ra-223 with ADT and SBRT for metastatic castrate sensitive prostate cancer (mCSPC) patients. Each treatment agent on this study independently increases fracture risk. Ra-223 alone was shown to increase fracture risk in the REASURE study, a prospective trial on fracture risk in patients receiving Ra-223 monotherapy. For the Ra-223 cohort (n=36), 74 new fractures were identified in 20 patients (56%) at a median follow-up of 16.3 months, while for the reference cohort (n=36), 16 new fractures were identified in 12 patients (33%) at a median follow-up of 24 months [34]. Radiation therapy is also associated with a high incidence of fractures. A meta-analysis of 21 studies and 3929 patients with gynecologic cancers who received external beam radiation therapy found that pelvic insufficiency fractures occurred in 14% of patients, with 73.6% of fractures developing in the sacral bone or joint. The median time to fracture was 7.1 to 19 months post-radiation therapy [35]. The effect of ADT on fracture risk was described in a nationwide cohort study (n=144,670) in Korea, which showed that in patients with prostate cancer, ADT significantly increases the risk of newly developed fractures (HR, 1.815; 95% CI, 1.703–1.935; $p < 0.0001$) and osteoporosis (HR, 1.381; 95% CI, 1.305–1.461; $p < 0.0001$) compared to those not receiving ADT, and this is positively correlated with the duration of ADT [36].

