Patients receiving androgen deprivation therapy (ADT) and Radium-223 (Ra-223) in combination face a significantly increased risk of non-pathological fractures. The phase 3 ERA 223 study on metastatic castrate resistant prostate cancer (mCRPC) patients was unblinded prematurely after an unplanned ad-hoc analysis revealed significantly increased fracture rates with the addition of Ra-223 to treatment with abiraterone acetate and prednisone or prednisolone. While fractures of any grade occurred in 11% of patients receiving a placebo instead of Ra-223, this increased to 29% of patients for the group receiving Ra-223 [37]. 78% of all fractures occurred at uninvolved sites, not metastatic sites.

BHAs have been shown to reduce the occurrence of fractures in this setting. On the ERA 223 study, the use of bone health agents (BHAs) was only allowed for patients who were on BHAs at baseline, which was around 40% of the study population. No patients were permitted to initiate BHA use while on study. They reported that in both the Ra-223 and placebo groups, patients on BHAs from baseline were associated with a lower fracture rate. For the Ra-223 group, fractures occurred in 15% of patients using BHAs, compared to 37% of patients not using BHAs. For the placebo group, fractures occurred in 7% of patients using BHAs, compared to 15% of patients not using BHAs [38].

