After the ERA223 trial reported the increased risk of fractures with the addition of Ra-223, the EORTC1333/PEACE III trial was amended to mandate that all patients must start using a BHA. This trial compared enzalutamide and Ra-223 to enzalutamide alone for mCRPC patients, and reported that when Ra-223 is combined with enzalutamide treatment, the risk of fracture significantly increases from 13% to 33%. They found that when BHAs are used a minimum of 6 weeks before the first administration of Ra-223, this risk is almost abolished [39]. The results of these studies necessitate BHA use in our present study, as Ra-223, ADT and SBRT are used in a combined treatment regimen. The need for BHA use is clearly demonstrated for mCRPC patients treated with ADT and Ra-223. BHAs like bisphosphonates and RANKL inhibitors are also indicated for use in mCSPC patients on ADT to prevent treatment-induced bone loss and resulting fractures at a dosage of 60 mg denosumab every 6 months or 5 mg zoledronic acid once per year, respectively [40]. Patients on this study will be required to take bisphosphonates or RANKL inhibitors to reduce the risk of fracture associated with Ra-223, ADT and SBRT.

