- e. *Cycle 1 Day 1*: With the exception of PSA, serum testosterone and blood counts other screening evaluations performed within 14 days prior to Cycle 1 Day 1 of protocol therapy may serve as Day 1 baseline evaluations.
- f. Participants must meet criteria in [Section 6.1](#) to initiate SBRT on Cycle 1 Day 1.
- g. Assessments must be performed **within 7 days** prior to radium Ra 223 dichloride. Safety assessments must be reviewed within 7 days prior to initiating a new cycle.
- h. *Cycle 2 Day 1 (1st dose of radium Ra 223 dichloride)*: Participants must meet criteria in [Section 6.2](#).
- i. *Post Ra-223/EOT visit to occur approx. 28 days +/- 7 days post-last dose of Ra 223 dichloride*.
- j. *Response follow-up* assessments for participants yet to progress, will occur ~ every 3 months (± 4 wks) (except [tumor evaluations](#)) from the day of last response evaluation until progression or the initiation of a new therapy.
- k. *Long-term follow-up* assessments for participants who progressed or ended Response Follow-up to occur annually (± 30 days) or as requested by the Study PI via medical record review, review of social security registry/ public records, and/or telephone call.
- l. *Informed consent* process to be fully documented (see [Section 17.4](#)). Informed consent must occur prior to any research only (non-SOC) screening procedures.
- m. *Medical history* to include a review of treatment history, any ongoing medical conditions and medical history pertaining to eligibility on study and involvement during study.
- n. *Eligibility criteria* are detailed in [Section 3.0](#).
- o. *Registration* into a COH clinical trial management system (CTMS).
- p. *Standard physical exam* includes weight and skin analysis.
- q. *Vital signs*: heart rate, blood pressure, respiration rate, and temperature.
- r. *Concurrent medications* and reason for administration to be documented in the EHR and eCRF from within 56 days prior to protocol therapy up to EOT visit. See [Section 5.11.1](#) for concomitant medication restrictions and guidelines.
- s. *Adverse event (AE)* will be assessed using CTCAE v.5.0.
- t. Active AE reporting will start from start of treatment until the post RA-223 visit/EOT visit **NOTE**: The highest AE grade per cycle will be reported in the eCRF from start of therapy until the EOT visit. **Exceptions to expedited reporting** are stated in [Section 8.2](#)

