- u. Long-term toxicities -- secondary malignancy, thyroid dysfunction-- attributed to protocol therapy will be collected via medical record review and/or phone call during Response Follow-up, standard of care visits and Long-term Follow-up. **NOTE**: If the participant is no longer at COH, the study team will request relevant medical information from the external institution.
- v. If clinically indicated by history of cardiovascular disease.
- w. *Serum chemistry* panel to include: glucose, Blood Urea Nitrogen (BUN), creatinine, total protein, albumin, magnesium, bicarbonate, calcium, sodium, potassium, chloride, total bilirubin, alkaline phosphatase, ALT and AST.
- x. *Immune biomarker studies*: Collect 20 mL per timepoint in sodium heparin green-top tubes and store on ice until delivery to [name] laboratory (See [Section 10.2](#) for details). **NOTE**: Notification to the [name]'s laboratory of pending sample collection must be made **at least 1 day in advance** (see [Section 10.2.1](#) for details).
- y. *Tumor tissue*: If available, archival metastatic or primary tissue will be submitted for clinical testing. Refer to [Section 10.1](#) for additional details.

- z. *Fresh metastatic tissue (optional)*: If the participant is willing attempts should be made to take extra metastatic tissue for clinical testing at the time of standard of care biopsy. See also [Section 10.1](#).
- aa. *Tumor Evaluation*: Options include combination of: CT chest, abdomen, pelvis, CXR, targeted X-rays, bone scan, Whole Body MRI, MRI of the TLS spine, MRI of the pelvis, PET/CT. All anatomical areas of the body need to be included (chest, abdomen, pelvis, skeleton) using combination of these tests. Follow up scans should at the minimum include the same scans utilized for screening.
- bb. Tumor evaluation to occur every 6 months (\pm 14 days) from last tumor evaluation, and at PSA progression (unless taken within the last 4 weeks).
- cc. Refer to [Section 5.3](#) for the treatment plan. Refer to [Section 6.3](#) for dose modification/ delay guidelines and [Section 5.9](#) for supportive care guidelines.

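### Routine AE entry stops about 6.4 months after SBRT starts on the nominal schedule, and the follow-up rule then omits fracture, so non-serious late fractures have no recording rule

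*Combined protocol and SAP*

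**What the plan says.** **Routine collection.** Footnote t of the study calendar states: "Active AE reporting will start from start of treatment until the post RA-223 visit/EOT visit". Section 12.2 ends eCRF entry of the highest grade per cycle at the same visit. Footnote i places that visit about 28 days (plus or minus 7) after the last radium dose.

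**Collection in follow-up.** In both follow-up columns the AE row carries only footnote u, which covers long-term toxicities and names them: "secondary malignancy, thyroid dysfunction-- attributed to protocol therapy will be collected via medical record review", or by phone call. Fracture is not named.

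**General safety text.** Section 8.1 defines an AE as arising during or after treatment and gives no end date for collecting non-serious AEs or for reporting SAEs. Its SAE definition covers unplanned hospitalization, lasting disability, and events that may need intervention to prevent a listed outcome.

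**Why fracture matters here.** Section 2.5 says: "In particular, non-pathologic fractures are an area of concern". It adds that each treatment independently raises the risk. For external beam radiation in gynecologic cancers it reports: "The median time to fracture was 7.1 to 19 months post-radiation therapy". For a radium cohort it reports new fractures in 20 of 36 patients (56%) at a median follow-up of 16.3 months.

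**Objective.** Section 1.2 includes: "To assess long-term toxicities during 5-year follow-up in patients with oligometastatic castration sensitive prostate cancer".

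**The concern.** The protocol identifies one hazard as the particular worry, makes 5-year toxicity a secondary objective, and then writes a follow-up rule that leaves that hazard out. Section 7.5 lists vertebral compression fracture and fracture among the SBRT adverse events, and Section 7.4 lists fracture for relugolix. Thyroid dysfunction appears in none of the Section 7 lists, yet footnote u collects it. Bone agents may continue until testosterone recovers, so the plan does not treat the risk as ending with the last radium dose.

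The stake is the tolerability conclusion. Section 13.5 says tolerability will help guide further studies. A fracture count that is complete for about six months and afterwards holds only serious events would look low beside the rate in Section 2.5 that was seen at 16.3 months. A reader could take the difference as a sign of safety when part of it is a difference in how long fractures were recorded.

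**Working it through.** The plan gives no length for the AE window, so it has to be built from the visit schedule. One month is taken as 30.4375 days.

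**The plan's own duration (Section 13.3).** About 8 months of therapy plus 60 months of follow-up = 68 months. This agrees with 36 weeks of ADT: 252 / 30.4375 = 8.3 months.

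**The AE window.** Inputs: Cycle 1 Day 1 is the start of SBRT (day 0), cycles last 28 days, and radium is given on Day 1 of Cycles 2 to 7 (Section 5.2). Footnote d allows 28 ± 7 days per cycle.

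- Sixth radium dose, Cycle 7 Day 1: 6 × 28 = day 168.
- EOT visit: 168 + 28 = day 196; 196 / 30.4375 = 6.44 months.
- Using only the ±7 days on the EOT visit: 189 to 203 days = 6.2 to 6.7 months.
- Every cycle and the EOT interval at 21 days: 7 × 21 = 147 days = 4.8 months.
- Every cycle and the EOT interval at 35 days: 7 × 35 = 245 days = 8.05 months. Toxicity delays would lengthen this further.

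With 60 months of follow-up after a nominal EOT, observation totals 66.4 months. Footnote u is the calendar's rule for 60 / 66.4 = 90% of it.

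**Timing check 1: the radiation medians.** Nominal EOT (6.44 months) comes before the lowest cited median (7.1 months). If those medians applied here, at least half of fractures would fall after EOT whatever the shape of the distribution. At 8.05 months that statement fails for the low end. Assuming exponential onset, the share after EOT is 2^(−EOT/median):

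| EOT | median 7.1 months | median 19 months |
|---|---|---|
| 6.44 months | 53% | 79% |
| 8.05 months | 46% | 75% |

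**Timing check 2: the radium cohort.** Assume a constant hazard and treat 16.3 months as common follow-up. Then 20/36 = 0.556 and λ = −ln(1 − 0.556) / 16.3 = 0.0498 per month.

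- By 6.44 months: 1 − exp(−0.0498 × 6.44) = 27.4%. That is 0.274 / 0.556 = 49% of the fractures seen by 16.3 months, so 51% come later.
- By 8.05 months: 33.0%, or 59% of them, so 41% come later.
- Counting from the first radium dose (day 28), the nominal window is 168 days = 5.52 months: 24.0%, or 43% of them, so 57% come later.

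The two sources come from different populations, and both put the late share at roughly half or more on the nominal schedule.

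**The texts side by side.** Section 8.1 is general and open-ended. Footnote t and Section 12.2 are specific and set a stop for routine entry. Footnote u is specific about what follows and omits fracture. Staff following the calendar as written would have no instruction to enter a non-serious fracture after EOT. Footnote r also ends concomitant-medication documentation at EOT, so bone-agent use at the time of a later fracture may go unrecorded too.

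**The case against.** The strongest reply is that the protocol is not silent. Section 8.1 counts events after treatment as AEs and sets no end date, so a late fracture could still be recorded. Section 2.6 offers secondary malignancies only as an example, so footnote u's list may be illustrative. AE assessment is marked in both follow-up columns, and the 6-monthly scans may reveal fractures. This stands in part: the intent looks broader than the footnote. But the specific text in footnote t and Section 12.2 most naturally governs what is entered, nothing directs staff to record a fracture seen on a scan, and footnote u requires attribution to protocol therapy.

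A reader might infer that late fractures go unreported altogether, or that every non-hospitalized fracture is lost. The documents do not support either. SAE reporting has no end date, and its definition extends to disabling events and to those needing intervention to avert a serious outcome. The gap is the non-serious fracture.

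A reader might also infer that at least half of fractures must be missed, or work out how many of the 24 patients are affected. The first holds only on the nominal schedule and only if the cited medians apply; serious late fractures would also still be reported. The second would join timing from gynecologic pelvic radiation to fracture rates from castration-resistant patients on other drugs, plus a guessed serious share. The documents support no such figure.

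Finally, the stopping rule and primary endpoint are unaffected. That is correct: Section 13.4 counts fractures only in Cycles 2 and 3, inside the routine window.

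**Conclusion.** The gap is real and limited. After the EOT visit, nominally 6.4 months from the start of SBRT and about 8.0 months with 35-day intervals throughout, non-serious fractures have no specific collection rule, while serious fractures remain reportable under Section 8.1. A substantial share of fractures, plausibly about half, could fall in that later period. That rests on carrying over timing from pelvic radiation in gynecologic cancers and from a radium cohort, with constant hazard assumed for the cohort; the documents give no fracture timing for this regimen. Some of those late fractures would be serious and still captured, so the late share is not the share lost. The secondary objective on 5-year toxicity is weakened for the hazard the protocol itself singles out. No sample-size, power or type I error figure changes. The correction is worth making because it is so cheap.

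**What to change.** Add fracture to footnote u: any grade, regardless of attribution, with date, site relative to the SBRT field, whether pathological, and bone-agent use at the time. Collect it at the existing 3-monthly Response Follow-up visits, from the 6-monthly imaging already scheduled, and in the annual long-term record review. Add a sentence to Section 13.5 to report the number and timing of first fractures over follow-up; a cumulative incidence estimate is optional with 24 patients. Add a line to Section 8.1 pointing to footnotes t and u, so that the general and specific rules agree. Routine entry of other non-serious AEs can still end at EOT.

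The cost is one CRF item and a few lines of text, with no new visits or scans. The limitation is that record review after progression will find mainly symptomatic fractures, and later therapy will confound their attribution.

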5.2 Cycle Definition

In the absence of delay due to toxicity, each treatment cycle lasts 28 days.

Cycle 1 Day 1 is defined by the administration of SBRT.

Cycles 2-7 Day 1 is defined by the administration of radium Ra 223 dichloride.

Post Ra-223 is defined as approximately 28 days post-last dose of radium Ra 223 dichloride.

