13.4 Stopping Rules for Excessive Toxicity

The stopping rules for safety/toxicity will be assessed for each patient after the first 2 cycles of radium dichloride 223. The expected rate of unacceptable toxicity should not be $\geq 33\%$.

A patient will be deemed to have experienced an Unacceptable Toxicity (UT) if any of the following occur during the **first 2 cycles of radium Ra 223 dichloride (Cycles 2 and 3)** and are attributed as possibly, probably, or definitely related to protocol therapy:

- **Hematological**
 - Any \geq Grade 3 hematological toxicity that delays the next planned dose of radium Ra 223 dichloride by > 28 days

○ *Non-hematological*

- Any >Grade 2 fracture
- Any \geq Grade 3 non-hematological toxicity that does not resolve to \leq Grade 2 with adequate supportive care and delays the next planned dose of radium Ra 223 dichloride by > 28 days
- Any recurrent \geq Grade 3 toxicity

The following table will be consulted as relevant toxicities defined above are encountered.

When a stopping rule is triggered, the study PMT will review and assess the safety of the trial and submit a report to the COH DSMC. The COH DSMC will review for approval any decision to continue accrual, amend the protocol, or permanently suspend accrual to the trial.

# of patients treated that determines early stopping	# of patients with unacceptable toxicity	Given the following toxicity rates, cumulative probability of early stopping:		
		10%	25%	35%
≤ 6	2	0.11	0.47	0.68
≤ 10	3	0.14	0.56	0.80
≤ 12	4	0.14	0.58	0.81
≤ 15	5	0.14	0.59	0.83
≤ 18	6	0.14	0.60	0.85
≤ 21	7	0.14	0.61	0.86
< 24	8	0.14	0.61	0.86

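### Fracture is the safety concern the protocol singles out, but it is not on the list of toxicities collected after the end-of-treatment visit, so late fractures would be captured incompletely

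*Combined protocol and SAP*

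**What the plan says.** Section 2.5 (Bone Health Agents) states the worry directly: "In particular, non-pathologic fractures are an area of concern". It says that each of the three treatments raises fracture risk by itself, and it makes bone health agents mandatory for that reason. Section 7.5 lists fracture among the adverse events of SBRT.

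Collection is set in the footnotes to the Section 11.0 calendar.

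- Footnote t: "Active AE reporting will start from start of treatment until the post RA-223 visit/EOT visit". Section 12.2 ends the per-cycle grade reporting at the same visit.
- Footnote i places that visit: "visit to occur approx. 28 days +/- 7 days post-last dose of Ra 223 dichloride".
- Footnote u governs both follow-up columns: "Long-term toxicities -- secondary malignancy, thyroid dysfunction-- attributed to protocol therapy will be collected via medical record review and/or phone call".

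The stopping rule in Section 13.4 counts fractures above Grade 2 only during the first two radium cycles. Section 1.2 makes long-term toxicity over 5 years of follow-up a secondary objective.

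**The concern.** The toxicity that the protocol worries about most is missing from its instruction for what to collect in follow-up, while thyroid dysfunction, which appears in none of the Section 7 toxicity lists, is on it. The restriction to events attributed to therapy narrows collection further. A fracture in a man who has had ADT, SBRT and radium is hard to attribute.

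The cited evidence points to late events. For radiotherapy the protocol reports: "The median time to fracture was 7.1 to 19 months post-radiation therapy". If general collection stops earlier than that, a fracture rate computed at EOT would look too low as a statement about the regimen. The 5-year objective would then lack reliable data on the risk that most needs describing. Accrual is planned over 66 months (Section 13.3), so non-serious late fractures in early patients could also go unnoticed while later patients are still being enrolled.

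**Working it through.** **Reproducing the plan's figures.** Section 2.5 reports for the radium cohort: "74 new fractures were identified in 20 patients (56%) at a median follow-up of 16.3 months". With 36 patients, 20/36 = 55.6%. In the reference cohort 12/36 = 33.3%. Both agree with the text. Participant duration in Section 13.3 also agrees: 8 + 60 = 68 months.

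**When active collection ends.** Section 5.2: "In the absence of delay due to toxicity, each treatment cycle lasts 28 days". The sixth radium dose is on Cycle 7 Day 1.

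- From Cycle 1 Day 1: 6 × 28 + 28 = 196 days; 196 / 30.44 = 6.44 months.
- From the first radium dose: 5 × 28 + 28 = 168 days = 5.52 months.
- With every cycle and the visit 7 days late (both windows are in the calendar): 6 × 35 + 35 = 245 days = 8.05 months.
- Share of the observation period under active collection: 6.44 / (6.44 + 60) = 9.7%.

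**Share of fractures after EOT, radiotherapy figures.** On the planned schedule 6.44 is below 7.1. If a median in the cited range applies, more than half of the fractures fall after EOT by the definition of a median. For a size, assume exponential time to fracture: share after EOT = 2^(−EOT/median).

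| EOT (months) | median 7.1 | median 19 |
|---|---|---|
| 6.44 (planned) | 53% | 79% |
| 8.05 (all 7 days late) | 46% | 75% |

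Counting from the end of SBRT, taken as day 21, shortens the interval to 196 − 21 = 175 days = 5.75 months and gives 57% to 81%.

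**Number of patients, radium figures.** Assume a constant hazard h = −ln(1 − p)/t and cumulative risk F(x) = 1 − exp(−hx), with x measured from the first radium dose.

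- *With bone health agents.* Section 2.6 requires these agents here. Section 2.5 gives 15% with radium plus these agents, without a follow-up time, so t = 16 months is my assumption. h = 0.1625/16 = 0.01016. F(5.52) = 5.4%, or 1.3 of 24 patients. By month 16: 0.15 × 24 = 3.6 of 24. Share after EOT: 1 − 5.45/15 = 64%.
- *Radium monotherapy cohort.* p = 20/36, t = 16.3 months, which is the median follow-up and not a time to fracture. h = 0.811/16.3 = 0.0498. F(5.52) = 24.0%, or 5.8 of 24. By 16.3 months: 13.3 of 24. Share after EOT: 1 − 24.0/55.6 = 57%.

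The patient counts differ greatly between the two rates, but the shares hardly move. That similarity is mostly a product of the constant-hazard assumption: for a low rate the share tends to 1 − 5.52/16 = 66%. The radium figures therefore give counts but say little about timing. Evidence on timing comes only from the radiotherapy range.

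**The case against.** The protocol does not go silent after EOT. Section 8.1 defines an adverse event as one occurring during or after treatment, and it gives serious adverse event reporting a start but no end. A fracture causing an unplanned hospital stay of at least 24 hours or significant disability would therefore be reportable, whatever its attribution. Section 2.6 mentions secondary malignancy only as an example of long-term toxicity, which leaves the list open. The calendar marks adverse event assessment in both follow-up columns. Response Follow-up includes an examination about every 3 months and imaging every 6 months that must cover the skeleton. Mandatory bone health agents should lower the number of fractures. No fracture-rate endpoint is defined, and the primary endpoint and sample size are untouched.

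Much of this stands, and it rules out some stronger readings. A reader might infer that most fractures would go unrecorded. The documents do not support that: a fracture after EOT is not thereby unrecorded, the timing range comes from another disease, and the share drops to 46% at its low end under permitted delays. A reader might also infer that the long-term toxicity objective cannot be answered. It can be, for secondary malignancy and thyroid dysfunction. Nor is the DSMC blind: under Sections 8.1 and 16.5 it receives status reports and toxicity data beyond the stopping rule. An early window for that rule is a design choice.

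What the objection does not supply is an instruction to record a non-serious fracture after EOT. Footnote u is the operative text for those columns. A compression fracture found on a scan, without admission or disability, need not qualify as serious, and nothing says that it is entered as toxicity. After progression or new therapy, follow-up becomes annual and rests on records or calls. Bone agents reduce the number of fractures but do not fill the gap in recording them.

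**Conclusion.** The concern holds in a limited form. Serious late fractures may be captured. Non-serious or non-attributed ones would be captured incompletely, so the fracture part of the 5-year toxicity objective could not be estimated reliably, and a rate cut off at EOT would look too low.

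The omission itself is a matter of text and needs no model. Its size does: 53% to 79% of fractures after EOT on the planned schedule, or 46% to 75% with maximal 7-day delays, assuming exponential times and medians borrowed from gynecologic pelvic radiotherapy. In patients, the 15% rate and an assumed 16 months give about 1.3 of 24 by EOT and 3.6 by month 16, so roughly two further patients. That rate comes from men with castration-resistant disease also receiving abiraterone. These figures show scale and are not predictions.

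This should be fixed, because fracture is the named risk and the remedy is cheap. It does not threaten the primary analysis.

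**What to change.** - Add fracture, regardless of attribution, to footnote u and to the Response and Long-term Follow-up forms. Record date, site, grade, pathological or not, inside an SBRT field or not, and bone-agent use at the time. The last item needs its own field, because footnote r ends medication recording at EOT.
- State in Section 8.1 when serious adverse event reporting ends.
- Reconcile footnote u with the open wording on long-term toxicity in Section 2.6 and with the adverse event definition in Section 8.1.
- Include the running fracture count in the reports already sent to the DSMC.

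The cost is one revised footnote, a few form fields and a little more data entry at examinations, record reviews and calls that are already planned. Treatment, visits and the stopping rule are unchanged.
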